## 2.2 Amgen Investigational Product Background: Blinatumomab

Blinatumomab (BLINCYTO, AMG 103, formerly also known as MT103 or bscCD19xCD3) is a member of a novel class of bispecific antibody constructs called BiTE®, or “bispecific T-cell engagers” (Dreier et al, 2002, Schlereth et al, 2006). Blinatumomab is a BiTE® antibody construct with dual binding specificities. T-cells are bound by its anti-CD3 moiety, whereas B lymphoblasts and cells are bound by the anti-CD19 moiety. This unique feature of blinatumomab allows it to transiently connect malignant cells with T-cells, thereby inducing T-cell mediated killing of the bound malignant cell. In preclinical models, blinatumomab-mediated T-cell activation involves the transient release of inflammatory cytokines and proliferation of T-cells. The subsequent serial lysis of multiple malignant B cells by a single blinatumomab-activated T-cell closely resembles a natural cytotoxic T-cell reaction. In clinical studies, T-cell activation, B-cell depletion, and transient cytokine release have been observed in patients being evaluated.

Blinatumomab is approved in multiple regions for the treatment of Philadelphia chromosome-negative relapsed or refractory B-cell precursor acute lymphoblastic leukemia (ALL).

Detailed information on the nonclinical effects of blinatumomab, and its clinical effects in this patient population is provided in the current country-specific prescribing information for blinatumomab. The European Union Summary of Product Characteristics provides detailed product information for investigators in the European Union and in regions where blinatumomab is not currently approved. The United States (US) Prescribing Information provides detailed product information for investigators in the US.

Refer to the specific section of the Investigator’s Brochure for additional information related to the physical, chemical, and pharmaceutical properties and formulation(s).

## 2.3 Dose Selection

### 2.3.1 Pharmacokinetics

The PK of blinatumomab was assessed over a dose range from 5 to 90 µg/m^2/day following cIV administration in subjects with NHL. Mean concentration of drug at steady state values increased dose-proportionally over the dose range tested. The estimated mean clearance, volume of distribution, and terminal half-life were 2.29 L/hour, 4.84 L and 2.47 hours, respectively, in subjects with NHL (Study MT103-104 [Goebeler et al, 2016]). Since body size (weight or body surface area [BSA]) was not a factor affecting the blinatumomab PK, a fixed dosing regimen, instead of BSA based

Approved

dosing, is appropriate for the treatment in adults. The fixed dosing regimen has been tested in Study MT103-208 (Viardot et al, 2016) in patients with diffuse large B-cell lymphoma and showed comparable exposure levels as those with an equivalent BSA based regimen.

## 2.4 Rationale

[figure not shown]
The effect of blinatumomab in the treatment of NHL was tested in a dose escalation study (Study MT103-104 [Goebeler et al, 2016]). A dose dependent clinical response was observed and objective clinical responses were seen starting at 15  $\mu\text{g}/\text{m}^2/\text{d}$  (~28  $\mu\text{g}/\text{day}$ ) and peaked at 60  $\mu\text{g}/\text{m}^2/\text{d}$  (~112  $\mu\text{g}/\text{day}$ ). Due to transient cytokine release after initiation of treatment, a step-dosing regimen was implemented to minimize cytokine related adverse events. An effective step-dose regimen of 9  $\mu\text{g}/\text{d}$  (week 1)-28  $\mu\text{g}/\text{d}$  (week 2)-112  $\mu\text{g}/\text{d}$  (remaining weeks) following cIV infusion for 8 weeks was established for the treatment of diffuse large B-cell lymphoma in study MT103-208 (Viardot et al, 2016). In this study, the blinatumomab concentration levels following the cIV regimen will be used as a reference to guide dose selection of SC administration. The target SC dose for the treatment of NHL is a dose that can achieve a similar exposure (area under the curve) as that of 112  $\mu\text{g}/\text{d}$  dose under cIV. To facilitate the SC dose selection, PK simulation was performed with the PK parameters (clearance and volume of distribution) generated from human studies under cIV and an assumed bioavailability of 0.25 in humans which was an approximate average of bioavailability in mouse (0.35), rat (0.16), monkey (0.21) and pig (0.30) under SC administration.

The simulated PK profiles of cIV (9/28/112  $\mu\text{g}/\text{d}$ ) and SC every day (112/450) and twice a day ([BID] 56/225  $\mu\text{g}/\text{dose}$ ) are provided in Figure 3. Based on currently available information on bioavailability and exposure, 450 (or 225  $\mu\text{g}/\text{BID}$ ) is the estimated SC equivalent dose to the cIV 112  $\mu\text{g}/\text{d}$  dose.

The assumption will be examined in Period 1 of this study following the PK assessment in the cIV run-in phase and then SC administration.

The calculated bioavailability for SC administration, the PK profiles of SC as well as safety and tolerability data will be used to assess the doses recommended for the Period 2 of the study.

**Figure 3. Simulated Blinatumomab Concentration-time Profiles Under Continuous IV Infusion and Under Once (1a) or Twice (1b) Daily Subcutaneous Administrations**

Abbreviations: BID = twice a day; cIV = continuous intravenous; Css = concentration of drug at steady state; IV= intravenous; SC = subcutaneous; QD = every day

## 2.5 Immunogenicity

Anti-blinatumomab antibodies (ADA) have been detected in a very limited number of adult patients with relapsed or refractory ALL treated with blinatumomab via cIV. No anti-blinatumomab antibodies have been detected in subjects with NHL under cIV. The incidence of anti-blinatumomab antibodies with SC administration will be examined in this study.

## 2.6 Rationale for SC vs cIV Route of Administration

The SC delivery could simplify administration and improve convenience, and has been assessed for rituximab, veltuzumab, trastuzumab, and alemtuzumab in various cancer settings (Goldenberg, et al, 2010, Pivot, et al, 2013, Stilgenbauer, et al, 2009, Shpilberg, et al, 2013). The SC delivery could also reduce the incidence of severe administration related reactions and costs (De Cock, et al, 2013, Lundin, et al, 2002), as well as avoid the need for a central line, potentially decreasing the risk of infection.

## 2.7 Clinical Hypotheses

Blinatumomab administered through the SC route will demonstrate a tolerable safety-profile with serum concentrations comparable to those for which efficacy was shown with cIV administration in subjects with indolent relapsed/refractory NHL.

## 3. EXPERIMENTAL PLAN

### 3.1 Study Design

The overall study design is described by study schemas in Figure 1 and Figure 2 at the end of the protocol synopsis section.

This is a global multi-center, Phase 1b open-label study investigating the safety and PK of blinatumomab administered subcutaneously for the treatment of relapsed/refractory indolent NHL. The SC administration of blinatumomab will be tested for the first time in humans.

Approximately **30** subjects' evaluable for dose limiting toxicities (DLT) will be enrolled in Period 1 (6 evaluable subjects in each dose-cohort). The focus of this period is to determine the PK, bioavailability, and safety profile of blinatumomab SC administration. The PK and bioavailability data from Period 1 of the study will be used in conjunction with safety data (DLT) to determine the SC MTD. The MTD or the maximum tested dose, if MTD is not reached, will be further tested in Period 2 in an expanded cohort of up to 15 additional **evaluable** subjects. Efficacy of blinatumomab administered subcutaneously will also be investigated in each period of the study.

### 3.1.1 Cycle 1/Period 1

In Period 1, **3 or more** separate dose cohorts of up to 6 DLT evaluable subjects each will be enrolled. Subjects will undergo an initial cIV blinatumomab run-in period (weeks 1 to 3) followed by **a 12-hour treatment free period, and then receive** SC administration (week 4). After **a treatment free period of 2 to not more than 3 days**, subjects receive cIV treatment to complete 6 weeks of therapy (weeks 5 to 6) **Figure 1**.

For all cohorts, the initial cIV dose of blinatumomab will be 9 µg/day for the first 7 days (to mitigate for potential cytokine release syndrome [CRS] and neurologic events associated with introduction to blinatumomab) which then will be escalated (dose-step) to 28 µg/day starting on day 8 through day 14 (week 2), and to 112 µg/day starting on day 15 until day 21 (week 3).

**After stopping cIV blinatumomab, there is a 12-hour treatment free period before starting SC blinatumomab.**

SC blinatumomab **starts after the 12-hour treatment free period and will be** administered (week 4) as the following dose-cohort levels:

- Dose Cohort 1: 112 µg q12h × 5 days (n = 6) for a total of 9 doses
- Dose Cohort 2: 225 µg q12h × 5 days (n = 6) for a total of 9 doses

(Note: A total of 9 SC doses will be given for the q12h dosing, so intensive PK samples can be obtained on day shift to reduce errors)

Approved

- Dose Cohort 3: 450 µg q24h × 5 days (n = 6) for a total of 5 doses
- **Additional Dose Cohorts: Dose level and dosing frequency to be determined as described below**

One or more dosing regimens may be selected based on clinical findings including safety, tolerability, and PK results from previous cohorts; after DLRT review, the DLRT may make recommendations for the next SC cohort dose and frequency. The dose may be increased (by 1 dose level or between the dose of the previous cohort and the next higher dosing level in [Figure 1](#) schema), kept at the same dose level or decreased by 1 or more dose levels. The dose frequency chosen (q12h, q24h, q48h, q72h, q96h, or q7 days) will be decided by the DLRT and will be based on the previous cohort PK data (refer to dosing schema [Figure 1](#)).

Once the SC dosing is complete, a treatment free period of 2 to not more than 3 days between stopping SC and restarting cIV will be observed. Then the cIV blinatumomab dosing will resume at 112 µg/day (weeks 5 to 6) to complete 6 weeks of treatment.

For each SC dose cohort, if  $\leq 1$  of the 6 DLT evaluable subjects experience a DLT during the SC administration DLT evaluation period then the dose will be determined to be tolerable and the **DLRT will decide the next dose level to be initiated and the frequency of administration for the next cohort**; see [Section 6.2.1.2.2](#) for definition of the DLT evaluation period.

For each SC dose cohort, if  $\geq 2$  of the 6 evaluable subjects experience a DLT during the SC administration then dosing will stop for individual subjects who experience a DLT, a DLRT meeting will be conducted, and further steps will be determined, **such as dose de-escalation or increasing dosing interval ([Figure 1](#))**. In addition, if subjects on this cohort have not reached the SC dosing, they will be allowed to stay on study but will finish cycle 1/period 1 as cIV.

MTD will be defined as the highest dose level at which  $\leq 1$  of 6 subjects experience a DLT. If no subject experiences a DLT, the MTD will be defined as the maximal dose tested.

For further details see [Section 6.2.1.2.1](#) and [Section 6.2.1.2.3](#).

Approved

### 3.1.2 Cycle 1/Period 2

The aim of Period 2 will be to assess the MTD as derived from Period 1, or the maximum tested dose, if MTD has not been reached, for additional safety and preliminary efficacy data in an expanded cohort of up to 15 evaluable subjects receiving SC treatment only (no cIV run-in) [Figure 2](#).

Doses for Cycle 1/Period 2 will be derived based on PK, bioavailability, and safety data collected in Cycle 1/Period 1 and DLRT review and recommendations. Subjects will receive the estimated SC equivalent doses **of the 2 lower cIV doses as given in the cIV blinatumomab run-in period sequentially: 2 doses of the equivalent SC dose to 9 µg/day of cIV during week 1, 3 doses of the equivalent SC dose to 28 µg/day cIV starting in week 1 and continuing into week 2, and then the SC MTD (or the maximum tested dose if MTD is not reached) and SC dosing interval as determined in Cycle 1/Period 1 starting in week 2 (day 12) and continuing to complete a total of 6 weeks of blinatumomab. See [Section 6.2.1.2.2](#) for definition of the DLT evaluation period for Period 2.**

**Continuous toxicity monitoring for early termination of the trial in Cycle 1/Period 2 will be performed. Termination of Cycle 1/Period 2 will occur if the posterior probability that the DLT rate is greater than 25% given the cumulative data thus far is at least 80%.**

The study endpoints are defined in [Section 10.1.1](#) and stopping rules are detailed in [Section 10.2](#).

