After completion of the initial cIV blinatumomab run-in period, **there is a treatment free period of 12 hours, then** SC blinatumomab will be administered **daily** for 5 days (week 4) **for dose cohort 1, 2, and 3. The SC dose and frequency will be chosen by the DLRT for further cohorts (see [Figure 1](#)).** After completing SC dosing there is **at least 2 days to not more than 3 days of no investigational product, followed by a return to investigational product at 112 µg/day cIV administration for 2 weeks (weeks 5 and 6) to complete a total of 6 weeks of therapy.** (Note: A total of 9 SC doses will be given for the q12h dosing, so intensive PK samples can be obtained on day shift to reduce errors).

#### 6.2.1.1.2 Cycle 1/Period 2

Subjects will receive the estimated SC equivalent doses of the 2 lower cIV doses as **given** in the cIV blinatumomab run-in period sequentially: **2 doses of the equivalent SC dose to 9 µg/day of cIV during week 1, 3 doses of the equivalent SC dose to 28 µg/day cIV starting in week 1 and continuing into week 2, and then the SC MTD (or the maximum tested dose if MTD is not reached) and SC dosing interval as**

determined in Cycle 1/Period 1 starting in week 2 (day 12) and continuing to complete a total of 6 weeks of blinatumomab (Figure 2).

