c Safety follow-up (EOS) should only be done following cycle 1 if treatment is ended after the 6 weeks of blinatumomab and no second cycle is planned to be administered. If a second cycle is planned then obtain the EOS after cycle 2.

- d Physical examination will include weight. Screening only: medical and surgical history, and height will **also** be obtained. Physical examination should be performed before the start of cIV infusion or dose increase, or before the subcutaneous injection, respectively.
- e Hospitalization during cIV administration in Period 1: at least 72 hours at the start of cIV and after each dose-step, as well as for at least 48 hours after **the return to cIV infusion after the SC dosing in Cycle 1/Period 1**. Hospitalization during subcutaneous administration: 5 days **SC administration**, and an additional 2 days **drug free (7 days total)**. NOTE: SC dosing should begin on a Monday (unless the study site can administer SC injections on the weekend).
- f The investigator should monitor the subject's vital signs continuously every 4 hours ( $\pm$  2 hours) during the first 12 hours after the start of each new treatment/dose-step. Subject must be in a supine position in a rested and calm state for at least 5 minutes before blood pressure assessments are conducted. If the subject is unable to be in the supine position, the subject should be in most recumbent position possible. The position selected for a subject should be the same throughout the study. Vital sign measurements will be repeated daily during the subject's hospitalization.
- g Serious adverse events are collected from the time of signing informed consent form to the end of study and adverse events are collected after the first dose of IP.
- h Serum or urine pregnancy test will be performed for all female subjects unless surgically sterile or > 2 years postmenopausal. Additional pregnancy testing may be performed at the investigators' discretion or as required per local laws and regulations.
- i Coagulation will include partial thromboplastin time (PTT), INR, and fibrinogen.
- j Lumbar puncture is only needed for disease assessment per standard of care per investigator. Lumbar puncture should be obtained for evaluation of seizures during blinatumomab treatment, if clinically stable, and a sample sent for blinatumomab PK.

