**Table 4. Cycle 1/Period 1 Investigational Product Dosing and PK Assessments for Week 4 and 5**

Study Part	Subcutaneous Administration (Doses tested sequentially in separate cohorts)							cIV to complete 6 weeks of treatment			
	22	23	24	25	26	27	28	29	30	31	37
Cycle Day											
Cycle Week	4							5			6
q12h											
Blinatumomab	X b	X b	X b	X b	X b	X b		X	X	X	X
Blinatumomab PK sample a	X c				X c	X c	X c		X d		
q24h											
Blinatumomab	X b	X b	X b	X b	X b	X b		X	X	X	X
Blinatumomab PK sample a	X c				X c	X c	X c		X d		
q48h											
Blinatumomab	X b		X b		X b			X	X	X	X
Blinatumomab PK sample a	X c				X c	X c	X c		X d		
q72h											
Blinatumomab	X b			X b				X	X	X	X
Blinatumomab PK sample a	X e			X e	X e	X e	X e		X d		
q96h											
Blinatumomab	X b				X b			X	X	X	X
Blinatumomab PK sample a	X c				X c	X c	X c		X d		
q7d											
Blinatumomab	X b							X	X	X	X
Blinatumomab PK sample a	X f	X f	X f	X f	X f				X d		

Abbreviations: cIV = continuous intravenous; CRS = cytokine release syndrome; CTCAE = Common Terminology Criteria for Adverse Events; PK = pharmacokinetic; q12h = every 12 hours; q24h = every 24 hours; q48h = every 48 hours; q72h = every 72 hours; q96h = every 96 hours; q7d = every 7 days; SC = subcutaneous

a Additional PK samples will be collected for adverse events of CTCAE ≥ grade 3 neuro toxicity and CRS occur throughout the study at the start, 24 hours after the event and at the resolution of the event. PK data will be collected for CTCAE ≥ grade 3 adverse events of CRS or neurotoxicity that occurs during SC administration. Obtain the samples as close as possible to the start of the event, at approximately 24 hours after the event and at the end of the event when all symptoms are resolved. Refer to [Section 7.3.15.1](#).

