b If a subject has a dose interruption during the SC administration period and that dose needed to be provided on a weekend, then the dose will be held and dosing will resume on the next business day if the site is unable to administer SC dosing on weekends due to local feasibility challenges. In that case, despite any extra days added due to treatment interruption in the cIV portion, day 22 still refers to the first day of SC administration.

c During SC dosing, at q12h, q24h, q48h, and q96h, PK samples are collected for the first dose on day 22 (pre-dose, as well as 1 hour ± 15 minutes, 2 hours ± 15 minutes, 4 hours ± 30 minutes, 6 hours ± 30 minutes, 8 ± 1 hours, and 12 ± 1 hour (before the next q12h dose if applicable) and for the last dose on day 26 (pre-dose, as well as post-dose at 1 hour ± 15 minutes, 2 hours ± 15 minutes, 4 hours ± 30 minutes, 6 hours ± 30 minutes, 8 ± 1 hours, 12 ± 1 hours, as well as 24 ± 2 hours (day 27), and 48 ± 2 hours (day 28).

d In the return to cIV dosing following the 5 treatment days of SC administration, PK samples are collected at any time during the day on the second day (day 30) after resuming 112 µg/day cIV dose (day 29). Refer [Section 7.3.15.1](#) for detail, sampling window and handling if dose interruption occurred.

e For the SC q72h dosing regimen, PK samples are collected for the first dose on day 22 (pre-dose, as well as 1 hour ± 15 minutes, 2 hours ± 15 minutes, 4 hours ± 30 minutes, 6 hours ± 30 minutes, 8 ± 1 hours, and 12 ± 1 hour and for the last dose on day 25 (pre-dose, as well as post-dose at 1 hour ± 15 minutes, 2 hours ± 15 minutes, 4 hours ± 30 minutes, 6 hours ± 30 minutes, 8 ± 1 hours, 12 ± 1 hours, as well as 24 ± 2 hours (day 26), 48 ± 2 hours (day 27), and 72 ± 2 hours (day 28).

f For the SC q7d dosing regimen, PK samples are collected for the dose on day 22 (pre-dose, as well as 1 hour ± 15 minutes, 2 hours ± 15 minutes, 4 hours ± 30 minutes, 6 hours ± 30 minutes, 8 ± 1 hours, and 12 ± 1 hour as well as 24 ± 2 hours (day 23), 48 ± 2 hours (day 24), 72 ± 2 hours (day 25) and 96 ± 2 hours (day 26).

Approved

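### For the q7d option in Cycle 1/Period 1, the limit of two to three treatment-free days before cIV restarts contradicts Table 4, which leaves 7 elapsed (6 whole) days

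*Protocol*

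**What the plan says.** Section 3.1.1 of the protocol states the rule: "a treatment free period of 2 to not more than 3 days between stopping SC and restarting cIV will be observed". Section 6.2.1.1.1 repeats it as "at least 2 days to not more than 3 days of no investigational product". The synopsis, Table 3 footnote p and SAP Section 3.1.1 carry the same range. None of these texts varies it by SC dosing interval, although Section 3.1.1 lets the DLRT choose any interval from q12h to q7d.

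The day-by-day schedule is in Table 4, titled "Cycle 1/Period 1 Investigational Product Dosing and PK Assessments for Week 4 and 5". Every row has cIV from day 29, and footnote d places the PK sample on day 30, "after resuming 112 µg/day cIV dose (day 29"). Footnote c, for q12h, q24h, q48h and q96h, ties the final PK series to the dose given then: "for the last dose on day 26". Footnote e puts the last q72h dose on day 25. Footnote f gives q7d one dose, on day 22, with late samples at "72 ± 2 hours (day 25) and 96 ± 2 hours (day 26").

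Three other places fix the same calendar. Section 3.1.1 puts the return to cIV in weeks 5 to 6. Section 6.2.1.3 and Table 1 require dexamethasone before cIV resumes on day 29. Section 6.2.1.2.2 makes the Period 1 DLT window the whole of week 4, 7 days.

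**The concern.** A gap rule written for a five-day SC course has been left in place for a regimen with one injection at the start of the week. Footnote d shows the same carry-over: it is attached to the q7d row but opens with "In the return to cIV dosing following the 5 treatment days of SC administration".

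The two instructions produce different data. Under Table 4, week 4 contains SC drug only, so DLTs in the window and the late PK samples describe the SC route. Under the gap rule, cIV at 112 µg/day would be running for part of the DLT window. The DLT definition in Section 6.2.1.2.3 asks whether an event is related to blinatumomab, not to a route, so it would not separate the two sources. The last SC samples, which inform the terminal slope described in SAP Section 10.7, would be mixed with infused drug. Six evaluable subjects decide whether a cohort is tolerable, so an ambiguity that applies to all six matters.

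**Working it through.** **Inputs.** Limit: 2 to 3 days (Sections 3.1.1 and 6.2.1.1.1). cIV restart: day 29 (Table 4 footnote d). Last SC day: 26 for q12h, q24h, q48h and q96h (footnote c), 25 for q72h (footnote e), 22 for q7d (footnote f). DLT window: days 22 to 28.

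**Two ways to count.** The protocol does not say which applies.
- Elapsed days = 29 − last SC day.
- Whole drug-free days = 29 − last SC day − 1. Table 3 footnote e counts this way: five SC days plus two days "drug free (7 days total"), that is, days 27 and 28 free after a last dose on day 26.

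**Reproducing the plan's figure.** A last dose on day 26 gives 29 − 26 = 3 elapsed days and 3 − 1 = 2 whole days. The stated range is met on both counts.

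| Interval | Last SC day | Elapsed days | Whole drug-free days | Within 2 to 3? |
|---|---|---|---|---|
| q12h, q24h (footnote c) | 26 | 3 | 2 | yes |
| q48h, q96h | 26 | 3 | 2 | yes |
| q72h | 25 | 4 | 3 | only on whole days |
| q7d | 22 | 7 | 6 | no |

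**A third count.** Suppose the dosing interval itself were regarded as treatment. The q7d dose would then cover up to day 22 + 7 = 29, leaving 0 free days, below the minimum of 2. The q96h dose on day 26 would cover up to day 26 + 4 = 30, past the restart. This reading does not rescue the rule either.

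**What the gap rule would imply for q7d.**
- Elapsed count: restart on day 22 + 2 = 24 or 22 + 3 = 25.
- Whole-day count: days 23 and 24 free, restart day 25; or days 23 to 25 free, restart day 26.
- DLT-window days on cIV, from restart to day 28: 5, 4 or 3 for a restart on day 24, 25 or 26. That is 3 to 5 of 7.
- The 96 h sample (day 26) falls on the restart day or later in every case. The 72 h sample (day 25) is affected for a restart on day 24 or 25, and is clear for day 26. When sample and restart share a day, clock time decides.

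**Scale of the PK effect, partly on assumptions.** With the clearance of 2.29 L/h in Section 2.3.1, cIV steady state is (112/24)/2.29 = 2.04 ng/mL. The SC residue at 96 h cannot be taken from the documents. Assuming a 450 µg dose, bioavailability 0.25, volume 4.84 L and an SC half-life of 8 to 19 h, it would be about 0.001 to 0.06 ng/mL, so infused drug would exceed it about 35-fold or more. The half-life range is an assumption, and no assay limit is given.

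**The case against.** The strongest reply is that nobody would restart cIV inside week 4. The weeks 5 to 6 wording, the day-29 premedication, the day-29 restart in Table 4 and the day-30 PK sample all agree; only the generic gap phrase fails to fit q7d. This largely stands. A reader might infer that q7d subjects will receive cIV during the DLT window; the documents do not support that, and the operating schedule points the other way. The reply does not remove the conflict. It concedes that the limit, stated repeatedly and without exception, cannot be met by a regimen the DLRT may choose.

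A reader might also infer that q72h breaks the limit. That follows only from subtracting dates (4 days). On the count in Table 3 footnote e, days 26, 27 and 28 are free, which is 3 days and within the range. The phrase about stopping and restarting can be read as elapsed time, so the convention needs stating, but a contradiction is not established.

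Finally, the q12h and q24h rows of Table 4, in the machine-read text, carry SC marks on days 22 to 27. It is tempting to conclude that the table prescribes six dosing days, with 6 q24h doses against 5 (20% more). Footnotes c and d, the dose totals in Section 3.1.1, Sections 6.2.1.1.2.1 and 6.2.1.4.2, and the PK times in Section 7.3.15.1 all indicate five days ending on day 26. The extra mark may be an artefact of reading the page. It should be checked against the original and is not claimed as an error.

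**Conclusion.** The point holds for q7d. The text allows at most 3 treatment-free days and Table 4 gives 7 elapsed or 6 whole days, so the limit is exceeded by at least 3 days on either count. This rests only on day arithmetic and on the absence of an interval-specific exception in the text; Figure 1 could not be read here and should be checked for one.

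The consequence is conditional. Following the gap rule would put 3 to 5 of 7 DLT-window days on cIV and compromise the 96 h sample, possibly also the 72 h sample. Following Table 4 would make every q7d subject a deviation from the written limit. Neither arises unless the DLRT selects q7d. The 35-fold concentration ratio is illustrative, and the conclusion does not depend on it. This is a drafting inconsistency worth correcting before a q7d cohort opens.

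**What to change.** Reconcile Sections 3.1.1 and 6.2.1.1.1, with the matching synopsis and SAP Section 3.1.1 text, against Table 4 and its footnotes. For each SC interval, the last SC day, the cIV restart day, the last SC PK sample and the end of the DLT window should agree. State whether treatment-free days are elapsed time since the last injection or whole days without drug; this settles q72h. Adapt the five-treatment-day wording of footnote d where it is attached to intervals that do not have five SC days. Check the day-27 marks in the q12h and q24h rows against the original page. Which schedule applies is for the sponsor to decide. The cost is a protocol clarification and a matching SAP edit, with no additional subjects.
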